#### **Consent Procedure**

We have uploaded the consent form

#### **Randomization Procedures**

Once consenting to the study, upon beginning the REDCap screening survey, potential participants will automatically be randomly assigned to one of three conditions. This random assignment will not impact their screening process, eligibility, or the consent process. Their randomly assigned condition will not be revealed to them until after they consent to the study. Upon their consent, the information will be delivered to them via email, informing them of their assigned condition, outlining the study tasks and payment structure.

The three conditions are as follows: Control condition with psychoeducational reading material, a DIY worksheet, or a DIY tool with artificial intelligence, and are all concerned with the idea of thinking traps and learning how to apply the concept of cognitive reframing to situations in one's own life. Folks in both DIY tool conditions will be prompted to use their tools 3x a week, and all participants will be asked to respond to weekly surveys for the duration of 4 weeks.

## **Conditions:**

Version 2.4

#### DIY Tool with AI

This tool uses AI to help users learn about thinking traps and cognitive reframing, and practice applying these concepts to situations in their own life. Participants will be asked to describe a thought and a situation they are struggling with. They will then identify potential "thinking traps" (or cognitive distortions) in the thought and reframe it in a way that is more positive, realistic, or helpful. The tool uses artificial intelligence to help generate

reframed thoughts. Please refer to the document With-AI-DIY-Tool-Static-Pages.pdf that has been uploaded to zipline.

- **Metadata collection:** We will use metadata, which consists of passive data that is curated from the host site for the DIY tool and describes engagement patterns from the DIY tool. This metadata includes the length of time spent on the measure, percentage of measure completion, counts of tool visits and frequency of visits

## DIY Tool (no AI)

3x weekly, participants will be prompted to use the DIY tool which covers the concept and practice of cognitive restructuring using the same framework as from the DIY tool with AI, however without the AI component, as shown in the document Without-AI-DIY-Tool-Static-Pages.pdf that has been uploaded to zipline.

- **Metadata collection:** We will use metadata, which consists of passive data that is curated from the host site for the DIY tool and describes engagement patterns from the DIY tool. This metadata includes the length of time spent on the measure, percentage of measure completion, counts of tool visits and frequency of visits

## **Control Psychoeducation**

At the start of participation after consenting, participants in the control condition will be asked to read the psychoeducation materials that describe types of cognitive restructuring and tips for practicing them in the document DIY Study – Psychoeducation.docx that has been uploaded to zipline.

5.2 Recording	gs. Does the research involve creati	ng audio or video recordings?	
No	→ If no, go to question 5.3.		
X Yes	Yes $\rightarrow$ If yes, verify that you have described what will be recorded in 5.1 and answer question a .		
<del></del>		sent for being recorded be obtained from subjects and any other	
	individuals who may be re	ecorded?	
		nail [contact] before submitting this application in Zipline. In il, include a brief description of the research and a note that	
		als will be recorded without their advance consent.	
	X Yes		

(5.3) MRI scans. Will any subjects have a Magnetic Resonance Imaging (MRI) scan as part of the study procedures?

This means scans that are performed solely for research purposes or clinical scans that are modified for research purposes (for example, using a gadolinium-based contrast agent when it is not required for clinical reasons).

X No → If no, go to question **5.4**.
Yes → If yes, answer questions **a** through **c**.

a.	Describe	the MR	scan(s	). S	pecifically	y :
----	----------	--------	--------	-------------	-------------	------------

- What is the purpose of the scan(s)? Examples: obtain research data; safety assessment associated with a research procedure.
- Which subjects will receive an MRI scan?
- Describe the minimum and maximum number of scans per subject, and over what time period the scans will occur. For example: all subjects will undergo two MRI scans, six months apart.

b. l	Jse of gadolinium. Will any of the MRI scans involve the use of a gadolinium-based contrast agent
	(GBCA?)

No Yes

→ If yes, which agents will be used? Check all that apply.

Brand Name	Generic Name	Chemical Structure
Dotarem	Gadoterate meglumine	Macrocylic
Eovist / Primovist	Gadoxetate disodium	Linear
Gadavist	Gadobutro	Macrocyclic
Magnevist	Gadpentetate dimeglumine	Linear
MultiHance	Gadobenate dimeglumine	Linear
Omniscan	Gadodiamide	Linear
OptiMARK	Gadoversetamide	Linear
ProHance	Gadoteridol	Macrocyclic
Other, provide name:		

1.) The FDA has concluded that gadolinium is retained in the body and brain for a significantly longer time than previously recognized, especially for linear GBCAs. The health-related risks of this longer retention are not yet clearly established. However, the UW IRB expects researchers to provide a compelling justification for using a linear GBCA instead of a macrocyclic GBCA, to manage the risks associated with GBCAs.

Describe why it is important to use a GBCA with the MRI scan(s). Describe the dose that will be used and (if it is more than the standard clinical dose recommended by the manufacturer) why it is necessary to use a higher dose. If a linear GBCA will be used, explain why a macrocyclic GBCA cannot be used.

2.) Information for subjects. Confirm by checking this box that subjects will be provided with the FDA-approved Patient Medication Guide for the GBCA being used in the research or that the same information will be inserted into the consent form.

	Confirmed	
c. MRI facility. At which facility(ies) will the MRI scans occur? Check all that apply.		
UWMC Radiology/Imaging Services (the UWMC clinical facility)		

DISC Diagnostic Imaging Sciences Center (UWMC research facility)
BMIC Biomolecular Imaging Center (South Lake Union research facility)
Harborview Radiology/Imaging Services (the Harborview clinical facility)
SCCA Imaging Services
Northwest Diagnostic Imaging
Other: identify in the text box below:

**Personnel.** For MRI scans that will be conducted at the DISC or BMIC research facilities: The role, qualifications, and training of individuals who will operate the scanner, administer the GBCA (if applicable), and/or insert and remove the IV catheter should be described in question **12.3**.

**5.4** Data variables. Describe the specific data that will be obtained (including a description of the most sensitive items). Alternatively, a list of the data variables may be uploaded to *Zipline*.

## Phase 1

Both MHA and TS collect information from consumers about their demographics such as age, gender, marital status, race/ethnicity, income status and education. MHA and TS also collect these symptom measures at initial engagement with services:

- PHQ9 (depression),
- GAD7 (anxiety),
- Prodromal Questionnaire-Brief Version (PQ-B; psychosis);
- Brief Bipolar Test;
- SWED (eating disorders),
- PC-PTSD (PTSD),
- CAGE-AID (Substance Use Disorder);
- Work Health Survey,
- caregiver status, and the
- Duke Social Support Scale, a measure of perceived social support.

These measures have been uploaded to Zipline.

Phase 1 Talkspace Survey: Demographics (e.g., age, race, ethnicity, education, income, household size, health status, and language); Device usage; Opinions on sample language for push notifications; Opinions on how push notifications and specific language in those notifications impact or may impact their utilization of TS services

## Meta-Data

To document engagement patterns, we will use meta-data (MD), which consists of passive data that is curated from each website and describes how consumers initiate, use and disengage from DMH services. Meta-data includes behaviors such as click throughs to pages and links, time spent on a page, mouse/cursor movement between screening and material selections on a webpage, number of text interactions, time texting, and time between texts. These data are collected on the order of milliseconds (cursor hovers), seconds (clicks), minutes (page views, time between sessions), and hours, days, weeks (number of texts, visits over time).

## Phase 2

Data collected in Phase 2 MRTs will include meta-data and content data. Meta-data includes behaviors such as click throughs to pages and links, time spent on a page, mouse/cursor movement between screening and material selections on a webpage, number of text interactions, time texting, and time between texts. These data are collected on the order of milliseconds (cursor hovers), seconds (clicks),

minutes (page views, time between sessions), and hours, days, weeks (number of texts, visits over time). Content data includes survey measures, transcripts (TS only), demographics, type of articles/resources accessed. Talkspace transcripts are of message-based therapy interactions. All identifiable information (e.g., names, usernames, links) are scrubbed from the transcripts by an automated process internal to TS prior to transfer to UW. Additional anonymization occurs on secure servers at UW including generalizing specific mentions of places (e.g., changing Seattle to Pheonix or Duluth) and proper nouns (e.g., changing UW to USC), and adding or removing filler words with less unique word choices or phrases (e.g., changing 'My girlfriend's XBOX playing irritates me' to 'My sister's game playing makes me angry'). These methods are outlined in our Data Security Protocol (previously uploaded to Zipline).

## Phase 3

Data collected in Study 1 and Study 2 of Phase 3B will both include metadata from MHA and content/survey data. Meta-data includes behaviors such as click throughs to pages and links, time spent on a page, mouse/cursor movement between screening and material selections on a webpage, number of text interactions, time texting, and time between texts. These data are collected on the order of milliseconds (cursor hovers), seconds (clicks), minutes (page views, time between sessions), and hours, days, weeks (number of texts, visits over time). At initial engagement for Study 1, the PHQ-9 and for study 2, either the PHQ or GAD measures will be collected on the MHA website. The following describes more specific data variables for each study:

## Study 1 –

- PHQ-9
- Mini quiz/next steps quiz--two items, collecting the participant's primary website action intention. The first question asks, "What is the main thing you want to do after taking this mental health test" and answer choices such as "Take another mental health test", "Understand what depression is like", "Find a treatment provider near you". The second question asks "Do you feel like you need to do something to improve your mental health?" (Yes, No, Don't know)

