## Phase 3:

Study 1 (SMART): We will use a Sequential Multiple Random Assignment Trial (SMART) with an expected 50,000 users, with the goal of optimizing engagement strategies so that web users engage with MHA resources most relevant to their needs, including psychoeducation, links to treatment providers, or self-help tools. Participants will be randomized to type of screening results language, with conditions including results-as-usual, or tailoring by: 1) demographics (race, LGBTQ status, age) or 2) mental health severity (screening results) & perceived need. Subsequent randomization will determine whether single-item self-help tools embedded in content pages serve to engage users in active mental health strategies. Participants will be MHA consumers who land on the PHQ-9 mental health test page on the MHA website.

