## **Randomization sequence**

The drafted randomization sequence is outlined on the MHA SMART Flow.pdf uploaded to zipline. Participants will be randomized first between a standard demographics survey to start or demographics along with a mini quiz focusing on asking a participant's primary website action intention (e.g., reading more about depression, connecting with therapists, using a DIY tool) and perceived need to do something to improve their mental health. Participants will then be randomized to types of screening results pages, with combinations of tailored responses and resources based on their responses to the demographics quiz and/or the mini quiz. For instance, if the participant chooses to continue to visit further content, they will be randomized to conditions of different presentations of a DIY question or tool on the page. Length of engagement, bounce rates, and other variables listed under metadata collection will be used to examine the impact of tailoring on engagement, which conditions and combinations of conditions result in increased engagement, and how the use of DIY tools impact engagement.

## Study 2

As previously proposed in Aim 3, we have developed an AI tool that uses machine learning / NLP / AI methods to personalize and tailor an intervention to improve engagement and completion outcomes. We focus on a specific, popular DIY tool (~10,000 users /month) that teaches cognitive restructuring. Our pilot work found that (1) engagement and completion rates on DIY tools can be low, and (2) a pilot AI tool had significantly higher engagement and completion rates. These differences may arise due to AI support, UI/UX/design differences, other factors, or a combination thereof. Additionally, the efficacy of the digital tool to improve mental health functioning is unknown. Study 2 will recruit 300 participants who will be randomly assigned to one of three groups for a longitudinal month-long study: twice-weekly DIY tool use with AI, without AI, or a control group.

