ENHANCING ENGAGEMENT WITH DIGITAL MENTAL HEALTH CARE

STUDY00010958

07/03/2024

NCT04507360

Aim 3B Statistical Analysis Plan. For Study 1, all research questions were examined via logistic regressions. We assessed whether participants' first condition (i.e., demographics survey or Next Steps survey) predicted the odds of disengagement. Within participants who completed the demographics survey, we examined whether the odds of disengaging and clicking a featured resource on the screening results page significantly differed for participants in the Tailored Resources to Demographics condition compared to control (i.e., Generic Response + Generic Resources). Within participants from the Next Steps survey condition, we tested whether engagement significantly differed for participants shown Tailored Response + Generic Resources, Generic Response + Tailored Resources to Desired Resources, and Tailored Response + Tailored Resources to Desired Resources compared to control. We aimed to identify the optimal tailoring strategy by comparing engagement across all tailoring conditions, with Tailored Resources to Demographics set as the reference group. For Study 2, research questions were examined via t-tests and Cohen's d effect sizes comparing engagement, short-term restructuring effectiveness, longer-term effectiveness (e.g., skill acquisition, reductions in depression and anxiety), and heterogeneous treatment effects by condition (i.e., control, DIY tool without AI, and DIY tool with AI).

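### Study 1's page contrasts name no covariate, although PHQ-9 (both survey arms) and the quiz answers (Next Steps arm only) are known before the results page and could sharpen the estimates

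*Protocol*

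**What the plan says.** **SAP, Aim 3B paragraph.** "For Study 1, all research questions were examined via logistic regressions". Two sets of contrasts compare results pages within a survey arm:

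- Demographics survey: "Within participants who completed the demographics survey, we examined whether the odds of disengaging and clicking a featured resource on the screening results page" differ between Tailored Resources to Demographics and control.
- Next Steps survey: "we tested whether engagement significantly differed for participants shown Tailored Response + Generic Resources" or either of two other tailored pages, each against control.

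Every contrast is described by condition. No covariate is named, and the models are not declared unadjusted. No alpha, target effect, power or missing-data rule is given for Study 1.

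**Protocol, section 5.1, Randomization sequence.** Users are "randomized first between a standard demographics survey to start or demographics along with a mini quiz". After that, "Participants will then be randomized to types of screening results pages, with combinations of tailored responses and resources based on their responses" to those questions.

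**Protocol, section 5.4, Phase 3.** The PHQ-9 is taken at initial engagement. The Study 1 list adds a "Mini quiz/next steps quiz--two items, collecting the participant's primary website action intention" and, in its second item, whether the user feels a need to act.

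**Protocol, section 4.1.** The questions and tests that Study 1 users meet on the site are optional.

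**The concern.** The results page reports the PHQ-9 and its tailored versions are built from the survey answers, so those answers come before the page. Relative to the page randomisation they are baseline values, and adjusting for them cannot bias the page contrast.

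They are plausibly prognostic. Someone who came to find a treatment provider and feels a need to act may well click or leave at a different rate from someone who does not. If so, a model with page alone leaves explainable variation in the error. At stake is precision in the page contrasts, above all in the Next Steps arm, which is split over four pages. A second matter is reproducibility: a reader of the SAP cannot tell whether the models are adjusted, or for what.

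**Working it through.** **1. Which covariates exist for which contrast**

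| Contrast | PHQ-9 | Intention and need |
|---|---|---|
| First condition (survey type) | not assessed here | no: the quiz is part of the randomised condition |
| Pages within the demographics survey | yes | no: never asked |
| Pages within the Next Steps survey | yes | yes |
| All tailored pages, demographics page as reference | yes | no: absent on one side |

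**2. Cell sizes (assumed)**

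Section 5.1, Phase 3, says "We will use a Sequential Multiple Random Assignment Trial (SMART) with an expected 50,000 users". No allocation ratio is stated. With equal splits:
- demographics arm: 50,000 / 2 / 2 = 12,500 per page;
- Next Steps arm: 50,000 / 2 / 4 = 6,250 per page.

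The plan has no power figure to reproduce. At two-sided 0.05 and 80% power (both assumed), 6,250 per page detects 0.80 points from a 2.2% rate, 1.49 from 9% and 2.36 from 32%. These rates come from past figures in section 1.8b and are not Study 1 assumptions. About 2,000 click-throughs a month over 3,000 × 30 screens gives 2.2%. Bounce rates of 91% and 68% leave 9% and 32% staying.

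**3. Gain by formula, no missing answers**

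If covariates explain a share R² of outcome variance, effective n = n/(1 − R²), so power ≈ Φ(2.80/√(1 − R²) − 1.96) from an 80% start.

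| R² (assumed) | 0.8% | 2% | 5% | 10% | 15% |
|---|---|---|---|---|---|
| Power | 80.3% | 80.8% | 82.0% | 84.0% | 86.0% |

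**4. Gain by simulation, 6,250 per page**

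| Outcome rate | R² | Unadjusted | Adjusted |
|---|---|---|---|
| 2.6% | 0.7% | 80.3% | 80.0% |
| 34% | 4.6% | 78.7% | 79.0% |
| about one third | about 9% | 79% | 83% |
| 36% | 15% | 67.7% | 75.3% |
| about one third | about 18% | 81% | 87% |

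Monte Carlo error is about 2 to 2.7 points per figure. The 36% row starts below 80%, so its gain of 7.6 points is not strictly comparable with the others.

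**5. Why a low rate limits R²**

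Take four equal intention groups clicking at 4%, 3%, 1% and 0.8% (mean 2.2%). The between-group variance is (1.8² + 0.8² + 1.2² + 1.4²)/4 = 1.82 squared points, or 0.000182. The total is 0.022 × 0.978 = 0.0215, so R² is about 0.8% despite a fivefold spread.

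**6. The nearest prognostic figure in the documents**

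Section 1.8b reports that the odds of Talkspace disengagement fall 3.3% per intake PHQ-9 point. The platform and outcome differ, so this is only a guide. If half the users scored 10 points above the other half (assumed), the log-odds would vary by ±5 × 0.0336 = ±0.168. At a 32% rate, R² ≈ 0.32 × 0.68 × 0.168² = 0.6%. PHQ-9 alone may therefore add little, and most of any gain would have to come from intention and need.

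**7. Missing answers**

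Complete-case fitting multiplies n by (1 − m), where m is the missing fraction, so the gain reverses once m exceeds R². At R² of 5%, power is 82.0%, 80.0%, 77.8% and 72.9% for m of 0, 5%, 10% and 20%. Simulated power with 20% missing completely at random:

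| R² | Unadjusted | Not-answered category | Complete case |
|---|---|---|---|
| 0.8% | 82% | 82% | 74% |
| 7% | 81% | 83% | 74% |
| 17% | 81% | 86% | 78% |

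**8. Effect scale**

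In the 36% row of step 4 the log odds ratio moves from 0.090 (SE 0.0373) to 0.107 (SE 0.0405). The adjusted odds ratio is conditional, a different quantity. Standardising restores the target: with a true difference of 2.35 points, the standardised estimate averaged 2.37 and the unadjusted 2.36. The standard deviation of the estimate fell from 0.80 to 0.78 points at R² of 7% and from 0.86 to 0.77 at 17%.

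**The case against.** The strongest reply is that nothing here is invalid. Randomisation makes the unadjusted contrast unbiased for the marginal effect, and its standard error already allows for chance imbalance. With 6,250 per page, the difference in a 50% covariate has a standard error of only √(2 × 0.25/6,250) = 0.9 points. With no target effect or power stated, no shortfall can be shown. This stands.

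It also stands that the size of the gain depends on assumed R² and outcome rates, and that the low click rate implied by section 1.8b points to no gain for a click outcome.

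A reader might infer more than the documents support:

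- *That the SAP commits to unadjusted models.* It is a one-paragraph summary. Condition as the only predictor is inferred from its silence.
- *That adjustment is free.* Default complete-case fitting on optional items can lose more than it gains, the odds ratio changes meaning, and the SAP is dated 07/03/2024 and written in the past tense, so covariates chosen now may be post hoc. The first two costs disappear under the method proposed below; the third does not.
- *That intention and need help every page contrast.* They are collected on one side of the first randomisation only.
- *That the Next Steps pages are the trial's smallest cells.* Section 5.1 describes a later randomisation to DIY presentations among only those users who continue to content.

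**Conclusion.** The point holds as a matter of precision and specification; it is not a validity defect. The SAP names no covariate for the page contrasts, while PHQ-9 in both survey arms, and intention and perceived need in the Next Steps arm, precede the page and can properly be used.

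The likely gain runs from about zero (click rate near 2%, or R² under 1%), through about 0 to 4 points of power (R² 5% to 9%), to about 6 to 8 points (R² 15% to 18%). This assumes equal allocation, about 6,250 users per Next Steps page, two-sided 0.05, unadjusted power of about 80%, and no complete-case deletion. The documents do not support calling the unadjusted tests biased or underpowered.

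**What to change.** State in the SAP, for the page contrasts within each survey arm:

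1. **Model.** Logistic regression on page plus pre-page covariates. Next Steps arm: PHQ-9 total, intention and perceived need. Demographics arm: PHQ-9 total and the demographics collected there.
2. **Missing answers.** A not-answered category, with no complete-case deletion. Since the answers precede the page, their absence cannot be caused by the page.
3. **Effect measure.** The standardised (marginal) risk difference and odds ratio, by g-computation.
4. **Exclusions.** No quiz item in the first-survey contrast or in the cross-survey comparison.
5. **Status.** If outcomes have already been seen, label the adjusted model post hoc and show it beside the unadjusted one.

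The cost is some SAP wording and a few lines of code, with no new data. The downside is a little more specification work and, if results are known, the weaker standing of a post hoc analysis.
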